8.2 DATA QUALITY ASSURANCE

A quality assurance audit/inspection of this trial may be conducted by the sponsor or sponsor's designees, by IRBs/IECs, or by regulatory authorities. The quality assurance auditor will have access to all medical records, the investigator's trial-related files and correspondence, and the informed consent documentation of this clinical trial.

The data management procedures to ensure the quality of the data are described in detail in the trial data management and analysis plan (TDMP) available in the TMF.

8.3 RECORDS

CRFs for individual subjects will be provided by the sponsor. For drug accountability, refer to Section [4.1.8](#).

ClinBaseTM

In the Human Pharmacology Centre (HPC) – Boehringer Ingelheim's Phase I unit – the validated ClinBaseTM system is operated for processing information and controlling data collected in clinical studies. In addition to its function as a procedure control system, ClinBaseTM serves as data base. Instead of being entered into CRFs, selected data are directly entered into the system.

8.3.1 Source documents

Source documents provide evidence for the existence of the subject and substantiate the integrity of the data collected. Source documents are filed at the investigator's site.

All data reported in the CRFs must be consistent with the source data or the discrepancies must be explained.

Data directly entered into ClinBaseTM (that is, without prior written or electronic record) are considered to be source data. The place where data is entered first will be defined in a trial specific Source Data Agreement. The data in ClinBaseTM are available for inspection at any time.

The investigator may need to request previous medical records or transfer records, depending on the trial.

8.3.2 Direct access to source data and documents

The investigator/institution will permit trial-related monitoring, audits, IRB/IEC review and regulatory inspection, providing direct access to all related source data/documents. CRFs and all source documents, including progress notes (if applicable) and copies of laboratory and medical test results must be available at all times for review by the sponsor's clinical trial monitor, auditor and inspection by health authorities (e.g. FDA). The Clinical Research Associate/on site monitor and auditor may review all CRFs, and written informed consents. The accuracy of the data will be verified by reviewing the documents described in Section [8.3.1](#).

8.3.3 Storage period of records

Trial site:

The trial site must retain the source and essential documents (including ISF) according to the national or local requirements (whatever is longer) valid at the time of the end of the trial.

Sponsor:

The sponsor must retain the essential documents according to the sponsor's SOPs.

8.4 EXPEDITED REPORTING OF ADVERSE EVENTS

BI is responsible to fulfil their legal and regulatory reporting obligation in accordance with regulatory requirements.

8.5 STATEMENT OF CONFIDENTIALITY

Individual subject medical information obtained as a result of this trial is considered confidential and disclosure to third parties is prohibited with the exceptions noted below. Subject confidentiality will be ensured by using subject identification code numbers.

Treatment data may be provided to the subject's personal physician or to other appropriate medical personnel responsible for the subject's welfare. Data generated as a result of the trial need to be available for inspection on request by the participating physicians, the sponsor's representatives, by the IRB/IEC and the regulatory authorities, i.e. the CA.

8.6 COMPLETION OF TRIAL

The ethics committee / competent authority in each participating EU member state needs to be notified about the end of the trial (last subject / subject out, unless specified differently in Section [6.2.3](#) of the CTP) or early termination of the trial.

10. APPENDICES

Section [10.1](#) and [10.2](#) provides information on preparation of the intravenous stable labeled isotope BI 409306 (C-13/N-15) for infusion and its application.

10.1 DRUG SUPPLY AND EQUIPMENT

10.1.1 Drug supply

BI 409306 (C-13/ N-15) solution for infusion is an intravenous solution consisting of 6 mL of a sterile, clear, colourless solution, containing 0.1 mg/mL BI 409306 BS (C-13/N-15), and presented in a colourless glass vial sealed with a rubber stopper and an aluminum flip-off seal.

10.1.2 Disposables

Material	REF	Company
Mini-Spike ^{® 1)}	4550242	B Braun
Omnifix ^{® 2)} 10 mL Luer Lock Solo	4617100V	B Braun
Original Perfusor [®] Line Type: IV-Standard-PE, Luer Lock 150 cm ³⁾	8722935	B Braun
Discofix ^{® 3SC 4)}	4095111	B Braun
Introcan Safety [®] W Winged-FEP 18G ⁵⁾	4254562-01	B Braun
Combi-Stopper ⁶⁾	4495101	B Braun

¹⁾ Mini-Spike is a vented dispensing pin for withdrawing fluids from medication vials. Its integrated air-venting channel makes pressure-balancing techniques unnecessary.

²⁾ Omnifix 10 mL ,Luer Lock Solo – is a hypodermic syringe for single use with Luer Lock connection to allow the connection with the Perfusor[®] line.

³⁾ Original Perfusor[®] Line – tube for use with syringe pump “Perfusor^{® fm}”

⁴⁾ Dicofix^{® 3SC} is a stopcock system with axially and radially movable swivel lock for secure and speedy connection.

⁵⁾ Introcan Safety[®] is an intravenous catheter with protection against needlestick injuries.

⁶⁾ Combi-Stopper: sterile closing

Please note: only CE certified disposables are to be used.

10.1.3 Technical equipment

10.2 HANDLING INSTRUCTION

10.2.1 Overview

Prior to intravenous drug administration, 6 mL of the solution is withdrawn from the vials into a syringe “Omnifix® 10 mL Luer Lock Solo”. The application system is flushed with the solution for infusion.

Subsequently, 1 mL (i.e. 0.1 mg) of solution for infusion is administered over 30 minutes. Residual solution for infusion is discarded.

The following description provides a step by step instruction.

10.2.2 Preparation of i.v. solution for continuous infusion via syringe pump

- **Step 1:** Remove the flip-off seal from the glass vial containing BI 409306 BS (C-13/N-15)
- **Step 2:** Attach the Minispike® on the vial and mount the Omnifix® 10 mL Luer Lock Solo
- **Step 3:** Withdraw 6 ml i.v. solution completely
- **Step 4:** Disconnect the syringe from the Minispike®
- **Step 5:** Remove air bubbles from the Omnifix® 10 mL Luer Lock Solo if applicable
- **Step 6:** Connect the Perfusor® line with the filled Omnifix® 10 mL Luer Lock Solo
- **Step 7:** Connect the Discofix®3SC at the end of the Perfusor® line
- **Step 8:** Remove the air from the Perfusor® line by pushing the syringe plunger and fill the Perfusor® line and the Discofix®3SC completely with i.v. solution.
- **Step 9:** Put a Combi-Stopper to the Discofix®3SC for safe storage of the system until administration
- **Step 10:** Place the filled Omnifix® 10 mL Luer Lock Solo into the syringe pump Perfusor® fm
- **Step 11:** Flush the Perfusor® line **with 1 mL** via Perfusor® fm
- **Step 12:** Enter administration data into syringe pump Perfusor® fm:
1 ml solution is to be administered over 30 min.

Please note: The deadspace volume of Introcan Safety® W Winged-FEP 18G was determined as 0.1 mL. Therefore, the volume settings at the syringe pump must be increased from 1.0 mL to 1.1 mL (infusion duration 30 minutes).

The solution for infusion is ready for administration.

10.2.3 In-use stability

After withdrawal of i.v. solution from the glass vial, storage of vial and solution in the Omnifix® 10 mL Luer Lock Solo (including filled Perfusor® line) is allowed for 24 hours at

Proprietary confidential information © 2018 Boehringer Ingelheim International GmbH or one or more of its affiliated companies

room temperature. Vial and syringe shall be protected from direct sun exposure. No additional light protection measures are required.

10.2.4 Mode of application

The vials are for single use only. Remnants in vial and syringe must be discarded.

10.2.5 General remarks – important

The solution in the vial is ready for use. Because of lacking analytical coverage beyond the preparation procedure described in this document, no further dilutions of the solution is allowed.

Proprietary confidential information © 2018 Boehringer Ingelheim International GmbH or one or more of its affiliated companies

11. DESCRIPTION OF GLOBAL AMENDMENT(S)

Number of global amendment	1
Date of CTP revision	24 April 2018
EudraCT number	2017-004798-14
BI Trial number	1289-0025
BI Investigational Product(s)	BI 409306
Title of protocol	Absolute bioavailability and pharmacokinetics of BI 409306 using a single oral dose of BI 409306 co-administered with an intravenous stable labeled isotope BI 409306 (C-13/N-15) in healthy male and female subjects (Non-Randomised, open-label, single arm, single period design)
To be implemented only after approval of the IRB / IEC / Competent Authorities	
To be implemented immediately in order to eliminate hazard – IRB / IEC / Competent Authority to be notified of change with request for approval	
Can be implemented without IRB / IEC / Competent Authority approval as changes involve logistical or administrative aspects only	
Section to be changed	
1. 5.5.2.12. 4.1.4
Description of change	
1. The term “dipotassium” was replaced with the correct term “tripotassium”2. Clarification of position after oral drug administration
Rationale for change	
1. Correction2. Correction

Proprietary confidential information © 2018 Boehringer Ingelheim International GmbH or one or more of its affiliated companies

Number of global amendment	2
Date of CTP revision	04 May 2018
EudraCT number	2017-004798-14
BI Trial number	1289-0025
BI Investigational Product(s)	BI 409306
Title of protocol	Absolute bioavailability and pharmacokinetics of BI 409306 using a single oral dose of BI 409306 co-administered with an intravenous stable labeled isotope BI 409306 (C-13/N-15) in healthy male and female subjects (Non-Randomised, open-label, single arm, single period design)
To be implemented only after approval of the IRB / IEC / Competent Authorities	
To be implemented immediately in order to eliminate hazard – IRB / IEC / Competent Authority to be notified of change with request for approval	
Can be implemented without IRB / IEC / Competent Authority approval as changes involve logistical or administrative aspects only	
Section to be changed	
 1. 10.2.2 2. 3.3.3

2. LIST OF ABBREVIATIONS

Term	Definition / description
ADS	Analysis dataset
AE	Adverse event
AESI	Adverse event of special interest
ANOVA	Analysis of variance
AUC _{0-∞}	Area under the concentration-time curve of the analyte in plasma over the time interval from 0 extrapolated to infinity
BI	Boehringer Ingelheim
BWU	Bioavailability/Bioequivalence, within-subject design, uncontrolled w.r.t time
CI	Confidence interval
C _{max}	Maximum measured concentration of the analyte in plasma
CRF	Case report form
CTP	Clinical Trial Protocol
CTR	Clinical Trial Report
CV	Arithmetic coefficient of variation
DBLM	Database lock meeting
DILI	Drug induced liver injury
DNA	Desoxyribonucleic acid
ECG	Electrocardiogram
EudraCT	European Union Drug Regulating Authorities Clinical Trials
gCV	Geometric coefficient of variation
gMean	Geometric mean
ICH	International Conference on Harmonisation
iv	intravenous
LLT	Lower level term
Max	Maximum
MedDRA	Medical Dictionary for Regulatory Activities
Min	Minimum
N	Number non-missing observations
O*C	Oracle Clinical

Term	Definition / description
PK	Pharmacokinetics
PKS	PK parameter analysis set
PM	Poor metabolizer
po	Per os
PT	Preferred term
PV	Protocol violation
qd	Quaque die (daily)
R	Reference treatment
RAGe	Report Appendix Generator system
REP	Residual effect period
RPM	Report planning meeting
SAS®	Statistical Analysis System
SD	Standard deviation
SOC	System organ class
T	Test treatment
t _{max}	Time from dosing to maximum measured concentration of the analyte in plasma
TS	Treated set
TSAP	Trial statistical analysis plan
ULN	Upper limit of normal
WHO-DD	World Health Organization Drug Dictionary
XPKISTAT	Library of SAS® Macros for PK analysis

3. INTRODUCTION

As per ICH E9 ([1](#)), the purpose of this document is to provide a more technical and detailed elaboration of the principal features of the analysis described in the protocol, and to include detailed procedures for executing the statistical analysis of the primary and secondary variables and other data.

This Trial statistical analysis plan (TSAP) assumes familiarity with the Clinical Trial Protocol (CTP). In particular, the TSAP is based on the planned analysis specification as written in CTP Section 7 “Statistical Methods and Determination of Sample Size”. Therefore, TSAP readers may consult the CTP for more background information on the study, e.g., on study objectives, study design and population, treatments, definition of measurements and variables, planning of sample size, randomisation.

Study data will be stored in a trial database within the Oracle ClinicalTM (O*C) system.

Pharmacokinetic (PK) parameters will be calculated using Phoenix WinNonlinTM software (version 6.3, Certara USA Inc., Princeton, NJ, USA).

The statistical analyses will be performed within the validated working environment CARE, including SAS[®] (current Version 9.4, by SAS Institute Inc., Cary, NC, USA), and a number of SASTM-based tools (e.g., macros for the analyses of AE data or laboratory data; Report Appendix Generator system (RAGe) for compilation/formatting of the CTR appendices).

4. CHANGES IN THE PLANNED ANALYSIS OF THE STUDY

All analyses as planned in the CTP will be performed and are described in more detail in this TSAP.

5. ENDPOINTS

5.1 PRIMARY ENDPOINTS

Section 5.5.1.1 of the CTP: *The following primary endpoints will be determined for BI 409306 and BI 409306 (C-13/N-15):*

- $AUC_{0-\infty}$ and C_{max}

5.2 SECONDARY ENDPOINTS

5.2.1 Key secondary endpoints

This section is not applicable as no key secondary endpoints have been defined in the CTP.

5.2.2 Secondary endpoints

Secondary endpoints are pharmacokinetic parameters. For more details see CTP Section 5.5.1.2.

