3.3 SELECTION OF TRIAL POPULATION

It is planned that up to 12 healthy male and female subjects will enter the study. They will be recruited from the volunteers' pool of the trial site.

To explore potential differences in absolute bioavailability based on 2C19 metabolizer status, it is planned to include 6 subjects with CYP2C19 non-PM status, and up to 6 subjects with 2C19 PM status, if feasible.

A log of all subjects enrolled into the trial (i.e. having given informed consent) will be maintained in the ISF at the investigational site irrespective of whether they have been treated with investigational drug or not.

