7.3.2 Secondary analyses

As a sensitivity analysis, the ANOVA performed as primary analysis will be repeated with subject as fixed effect instead of random effect. The results will be presented in the same manner as for the primary analyses.

If an adequate number of PM subjects is reached within the study a subgroup analysis will be done for the primary PK endpoints to compare PM subjects with non-PM subjects.

The following descriptive statistics will be calculated for primary and secondary PK parameters and for further endpoints: N, arithmetic mean, standard deviation, minimum, median, maximum, arithmetic coefficient of variation, geometric mean, and geometric coefficient of variation. The data format for descriptive statistics of concentrations will be identical with the data format of the respective concentrations. The descriptive statistics of PK parameters will be calculated using the individual values with the number of decimal places as provided by the evaluation program. Then the individual values as well as the descriptive statistics will be reported with 3 significant digits in the clinical trial report.

The secondary parameters (refer to Section [5.5.1.2](#)) will be calculated according to the BI SOP 'Standards and processes for analyses performed within Clinical Pharmacokinetics/ Pharmacodynamics' ([001-MCS-36-472](#)).

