7.6 DETERMINATION OF SAMPLE SIZE

It is planned to enter up to 12 subjects in the trial: 6 subjects with CYP2C19 non-PM status, and up to 6 subjects with CYP2C19 PM status.

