6. GENERAL ANALYSIS DEFINITIONS

6.1 TREATMENTS

For basic study information on investigational products, assignment of treatments, and selection of doses, please see CTP, Sections 3 and 4.

The study will be performed as a non-randomised, open-label, single arm, single period trial with 2 treatments (T and R).

In total, it was planned to assign up to 12 healthy male and female subjects (6 subjects with CYP 2C19 non-PM status and up to 6 subjects with 2C19 PM status).

For details of dosage and formulation see Table 6.1: 1 and Table 6.1: 2 below:

Table 6.1: 1 Treatments and labels used in the analysis of AEs, safety laboratory data and vital signs as well as demographics

Treatment	Short label
A BI 409306 50mg tab + 0.1mg i.v.	BI tab + iv

Table 6.1: 2 Overview of treatments for intra-individual comparison

Treatment	Short label
T BI 409306, 50 mg tablet, qd	BI 50mg tab
R BI 409306 (C-13/N-15), 0.1 mg/mL i.v. solution 0.1 mg, qd	BI 0.1mg iv

The following separate study phases will be defined for the analyses of AEs:

- **Screening** (ranging from 0:00 h on day of informed consent until first administration time of study drug)
- **On treatment** (including residual effect period (REP);
- **Follow-up** (ranging from end of on treatment phase until 0:00 h on the day after trial termination date)

Displays of AEs will be presented without differentiation of intravenous or oral administration during on treatment phase.

Two types of AE displays will be provided in the report:

A) Section 15.3 and Appendix 16.1.13.1.8 (for ClinicalTrials.gov and EudraCT only) of the CTR displays:

In these displays, the on treatment phase will be analysed (labelled with the name of the study treatment (short label)). Screening and follow-up periods will not be included in this analysis.

B) Section 15.4 and Appendix 16.1.13.1.8 (except for ClinicalTrials.gov and EudraCT) of the CTR displays:

- Screening
- On treatment (labelled with the name of the study treatment (short label))
- Follow-up

In Section 16.1.13.1.8 AE tables, the following totals will be provided in addition:

- a total over all study phases ("Total")

Tables of vital signs and laboratory values will present results by the above mentioned on treatment phase.

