PROC GLM DATA=indata;
  CLASS subject treatment;
  MODEL logkp = treatment subject;
  LSMEANS treatment / PDIFF=CONTROL("Ref_trt") CL ALPHA=0.1;
  RUN;
```

Section 7.3.2 of the CTP: *If an adequate number of PM subjects is reached within the study a subgroup analysis will be done for the primary PK endpoints to compare PM subjects with non-PM subjects.*

This subgroup analysis will be done using the same model and parameters as for the primary analysis but including the PM status as a covariate (fixed effect).

The implementation for this analysis will be accomplished by using the XPKISTAT macro, based on PKS, option BWU (Bioavailability/Bioequivalence, within-subject design, uncontrolled w.r.t. time), and CLASSFIX=PM status.

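### The planned summaries of F, CL, Vz, t1/2, tmax and the mean concentration profiles pool PM and non-PM subjects, so none shows F or clearance by CYP2C19 status

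*SAP*

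**What the plan says.** Protocol 3.3 gives the reason for enrolling two genotype groups: "To explore potential differences in absolute bioavailability based on 2C19 metabolizer status". Protocol 7.6 plans "6 subjects with CYP2C19 non-PM status, and up to 6 subjects with CYP2C19 PM status".

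For the genotype comparison, Protocol 7.3.2 sets a condition, "If an adequate number of PM subjects is reached within the study", and a scope: "a subgroup analysis will be done for the primary PK endpoints to compare PM subjects with non-PM subjects". SAP 7.4 repeats this and builds the analysis "using the same model and parameters as for the primary analysis but including the PM status as a covariate (fixed effect"). No PM-by-formulation term is stated.

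The secondary endpoints in Protocol 5.5.1.2 are t1/2 and tmax for both analytes, CL and Vz for the intravenous tracer, and F for the oral drug. On these the SAP is brief: "Secondary endpoints are pharmacokinetic parameters. For more details see CTP Section 5.5.1.2". Protocol 7.3.2 and SAP 7 and 7.5.2 plan descriptive statistics for PK parameters and concentrations. Protocol 7.3.1 plans mean profiles. None of these places names CYP2C19 status as a grouping.

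Three other provisions bear on the point. AUC0-∞ and Cmax of the tracer are themselves primary endpoints (Protocol 5.5.1.1). Individual values of all subjects are listed by treatment, subject number and visit (SAP 7). CYP2C19 results go into the final report (SAP 5.4.2).

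**The concern.** F is the quantity the genotype recruitment is meant to inform, and it is a secondary endpoint. As planned, its descriptive summary is a single figure over 6 non-PM and anywhere from 0 to 6 PM subjects. The same holds for CL, Vz, t1/2, tmax and the mean profiles.

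If the genotypes differ, such a summary describes neither group. Its centre moves with the number of PM who happen to be recruited, and its gCV counts the genotype difference as between-subject variability. F by genotype would answer the stated exploratory question directly. CL by genotype would separate a difference in oral exposure into a bioavailability part and a clearance part.

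**Working it through.** The plan gives no figure to reproduce here beyond the count, 6 + up to 6 = up to 12, which adds up. It gives neither a PM/non-PM clearance ratio nor a variability for CL. Both are assumed below.

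**1. What a pooled summary of CL would show.** Let r be the PM/non-PM ratio of geometric mean CL (assumed 0.7 to 0.2), p the share of PM, n the number of subjects, and 30% the assumed within-group gCV.

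- Pooled geometric mean ÷ non-PM geometric mean = r^p. Pooled ÷ PM = r^(p−1).
- 6 PM (p = 0.5): 0.7^0.5 = 0.837 and 0.2^0.5 = 0.447, so 16% to 55% below non-PM. Against PM: 1.2 to 2.2 times.
- 2 PM (p = 0.25): 0.7^0.25 = 0.915 and 0.2^0.25 = 0.669, so 9% to 33% below non-PM. Against PM: 1.3 to 3.3 times.
- No PM (p = 0): ratio 1, no effect.

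Log-scale variance of the pooled sample = ln(1 + 0.3²) × (n−2)/(n−1) + p(1−p)(ln r)² × n/(n−1). With n = 12 and p = 0.5:

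- r = 0.7: 0.0862 × 10/11 + 0.25 × 0.1272 × 12/11 = 0.0783 + 0.0347 = 0.1130; gCV = √(e^0.1130 − 1) = 34.6%.
- r = 0.2: 0.0783 + 0.25 × 2.5903 × 12/11 = 0.0783 + 0.7064 = 0.7848; gCV = √(e^0.7848 − 1) = 109.2%.

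Allowing for sampling variation of the group means, by using ln(1 + 0.3²) without the factor 10/11, gives about 36% and 110%.

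**2. Whether the primary-endpoint subgroup analysis fills the gap.** Tracer CL = dose/AUC0-∞,iv = 1/AUC0-∞,norm,iv. The PM/non-PM ratio of geometric mean CL is therefore exactly the inverse of the ratio for tracer AUC0-∞, which is within the subgroup's scope. The question is whether the additive model returns that ratio.

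With complete data on 6 + 6 subjects, its two effects are plain averages of logs:

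- Formulation effect = √(F in non-PM × F in PM), which is the pooled F with or without the PM term.
- PM effect = √(tracer AUC ratio × oral AUC ratio).

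In a simulated 6 + 6 example, F was 0.307 in non-PM and 0.606 in PM, and the tracer AUC ratio was 1.865. The oral AUC ratio was then 1.865 × 0.606/0.307 = 3.68.

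- Formulation effect: √(0.307 × 0.606) = 0.431, which is neither group's F.
- PM effect: √(1.865 × 3.68) = 2.62, which is neither the tracer ratio nor the oral ratio.

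A model with a PM-by-formulation term returned 0.307 for non-PM and 1.865 for the tracer, hence a CL ratio of 1/1.865 = 0.54. The additive model as written supplies neither F nor CL by genotype.

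**3. What a split could deliver.** The 90% interval for the PM/non-PM ratio of CL has the factor exp{t(0.95, 4 + n_PM) × √ln(1 + gCV²) × √(1/6 + 1/n_PM)}. At an assumed gCV of 20%, 30% and 40% this is ×/÷ 1.23, 1.36 and 1.50 with 6 PM, and ×/÷ 1.30, 1.48 and 1.68 with 3 PM. That is coarse, but informative for a clear genotype difference.

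**The case against.** The strongest reply is that nothing is lost. With at most 12 subjects, every individual parameter listed and the CYP2C19 results in the report, a reader can rebuild each group by hand. This stands. A reader might infer that clearance will be reported only as a mixture, and the documents do not support that. The gap lies in the planned summary tables and mean profiles. Rebuilding from listings not sorted by genotype is still not a planned presentation.

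A reader might also infer that a genotype difference in F cannot be interpreted without CL by genotype. That does not follow either. F is a within-subject ratio of dose-normalised oral to intravenous AUC, measured in the same period. Under linear kinetics, systemic clearance cancels from it. CL by genotype is useful for explaining a difference in oral exposure, not for attributing a difference in F.

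Nor does the SAP table headed "Overview of treatments for intra-individual comparison" rule out a genotype split; it only labels treatments.

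Two further points stand. The trial is exploratory, tests no hypothesis and treats the secondary objectives descriptively, so no estimate or decision is biased by the layout. And a split may be specified elsewhere: Protocol 5.3 and SAP 6.4 and 7.6 are not in the available text, and SAP 7.5.2 defers to a sponsor procedure that is not available.

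**Conclusion.** The point holds for the available text. The secondary PK endpoints and mean profiles are summarised only over the genotype mix, and the additive PM covariate does not supply F or CL by genotype. The plan therefore has no summary that answers the exploratory question for which PM subjects are enrolled.

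The size is conditional. With 6 PM, a clearance ratio of 0.7 to 0.2 and 30% within-group gCV, all assumed, the pooled geometric mean CL misses the non-PM value by 16% to 55%. At the mild end the gCV rises only from 30% to about 35%. The figure of about 109% needs a five-fold clearance difference. If no PM is recruited there is no distortion.

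This is a worthwhile, inexpensive improvement in presentation. It does not show that data are lost, and it does not bear on the validity of the primary pooled estimate or the safety tables.

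**What to change.** In SAP 7.5.2 and Protocol 7.3.2, state that descriptive statistics of all PK endpoints, including F and CL, and the mean concentration profiles of both analytes are presented by CYP2C19 status (PM, non-PM) as well as overall. Do this whenever any PM is treated, independently of the unquantified condition for the subgroup model. If PM are few, show their individual values beside the non-PM summary.

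As a companion change, add a PM-by-formulation term to the subgroup model in SAP 7.4, or fit the groups separately, so that the inferential analysis also returns F by genotype. This does not replace the descriptive split, because t1/2, tmax, Vz and the profiles lie outside that model.

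The descriptive split needs a few lines of text and one grouping variable in tables and figures already planned. No new data are needed. The downside is small PM cells.
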